## **Dose-expansion phase**

There are no decision rules associated with this phase.

### **5.2. General Methods**

As described in Section 3.4, in this study ‘**treatment group**’ refers to one of the following:

- DL1 with lead-in: axitinib 5 mg oral BID followed by avelumab 10 mg/kg IV Q2W in combination with axitinib 5 mg oral BID, or
- DL-1A with lead-in: axitinib 5 mg oral BID followed by avelumab 5 mg/kg IV Q2W in combination with axitinib 5 mg oral BID, or
- DL-1B with lead-in: axitinib 3 mg oral BID followed by avelumab 10 mg/kg IV Q2W in combination with axitinib 3 mg oral BID, or
- DL1: avelumab 10 mg/kg IV Q2W in combination with axitinib 5 mg oral BID, or
- DL-1A: avelumab 5 mg/kg IV Q2W in combination with axitinib 5 mg oral BID, or
- DL-1B: avelumab 10 mg/kg IV Q2W in combination with axitinib 3 mg oral BID.

Baseline characteristics, disposition and efficacy data will be summarized based on the FAS by treatment group.

DLTs will be summarized based on the DLT-evaluable set by treatment group including data from the dose-finding phase only.

Other safety data, exposure data, concomitant medications and non-drug treatments will be summarized based on the safety analysis set by treatment group.

PK data will be summarized based on the PK analysis sets by treatment group.

Biomarker data will be summarized based on the biomarker analysis sets by treatment group.

Immunogenicity data will be summarized based on the immunogenicity analysis set by treatment group.

#### **5.2.1. Data handling after the cut-off date**

Data after the cut-off date may not undergo the cleaning process and will not be displayed in any listings or used for summary statistics, statistical analyses or imputations.

#### **5.2.2. Pooling of centers**

In order to provide overall estimates of treatment effects, data will be pooled across centers. The ‘center’ factor will not be considered in statistical models or for subgroup analyses due

to the high number of participating centers in contrast to the anticipated small number of patients randomized/treated at each center.

### **5.2.3. Presentation of continuous and qualitative variables**

Continuous variables will be summarized using descriptive statistics ie, number of non-missing values and number of missing values [ie, n (missing)], mean, median, standard deviation (SD), minimum, maximum and first and third quartile (Q1 and Q3).

Qualitative variables will be summarized by frequency counts and percentages. Unless otherwise specified, the calculation of proportions will include the missing category. Therefore counts of missing observations will be included in the denominator and presented as a separate category.

In case the analysis refers only to certain visits, percentages will be based on the number of patients still present in the study at that visit, unless otherwise specified.

### **5.2.4. Definition of study day**

Start day of study treatment is the day of the first dose of study treatment.

The study day for assessments occurring on or after the start of study treatment (eg, adverse event onset, tumor measurement) will be calculated as:

$$\text{Study day} = \text{Date of the assessment/event} - \text{start of study treatment} + 1.$$

The study day for assessments occurring prior to the first dose of study treatment (eg, baseline characteristics, medical history) will be negative and calculated as:

$$\text{Study day} = \text{Date of the assessment/event} - \text{start of study treatment}.$$

The study day will be displayed in all relevant data listings.

### **5.2.5. Definition of start of new anti-cancer drug therapy**

Start date of new anti-cancer drug therapy is used to determine the end of the on-treatment period (see Section 5.2.7).

The start date of new anti-cancer drug therapy is the earliest start date of anti-cancer drug therapy recorded in the 'Follow-up Cancer Therapy' eCRF pages that is after the first dose of study treatment. When start date of anti-cancer drug therapy is missing or partially missing, the imputation rules described in Section 5.3.3.4 should be applied using only data from the 'Follow-up Cancer Therapy' eCRF pages.

### **5.2.6. Definition of start of new anti-cancer therapy**

Start date of new anti-cancer therapy (drug, radiation, surgery) is used for censoring in efficacy analyses (see Section 6.2.2).

The start date of new anti-cancer therapy is the earliest date after the first dose of study treatment for the non-randomized phases or after the date of randomization for the randomized phase amongst the following:

- Start date of anti-cancer drug therapy recorded in the 'Follow-up Cancer Therapy' eCRF pages
- Start date of radiation therapy recorded in 'Concomitant Radiation Therapy', and 'Follow-up Radiation Therapy' eCRF pages with 'Treatment Intent' = 'Curative in intent'
- Surgery date recorded in 'Concomitant Surgery', and 'Follow-up Surgery' eCRF pages when 'Surgery Outcome' = 'Resected' or 'Partially Resected'.

When start date of anti-cancer therapy is missing or partially missing, the imputation rules described in Section 5.3.3.4 should be applied using 'Follow-up Cancer Therapy', 'Concomitant Radiation Therapy', 'Follow-up Radiation Therapy', 'Concomitant Surgery', and 'Follow-up Surgery' eCRF pages.

#### **5.2.7. Definition of on-treatment period**

Safety endpoints will be summarized based on the on-treatment period unless otherwise specified.

On-treatment period is defined as the time from the first dose of study treatment through minimum (30 days + last dose of study treatment, start day of new anti-cancer drug therapy – 1 day).

Safety data collected outside the on-treatment period as described above will be listed and flagged in listings but not summarized.

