9.6. Safety Analysis

Summaries and analyses of the primary safety endpoint will be based on the per protocol analysis set. All other summaries and analyses of safety parameters will include all patients in the safety analysis set. Safety data will be summarized by treatment group for all treated patients using appropriate tabulations and descriptive statistics separately for each phase of the study. Safety data collected during the lead-in PK period will be reported separately. All safety data collected through 90 days after the last administration of study drug will be listed.

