### 3.4. Baseline Variables

#### 3.4.1. Study drug, study treatment and baseline definitions

In this study ‘**study drug**’ refers to avelumab or axitinib and ‘**study treatment**’ (or ‘**treatment group**’) refers to one of the following:

- DL1 with lead-in: axitinib 5 mg oral BID followed by avelumab 10 mg/kg IV Q2W in combination with axitinib 5 mg oral BID, or
- DL-1A with lead-in: axitinib 5 mg oral BID followed by avelumab 5 mg/kg IV Q2W in combination with axitinib 5 mg oral BID, or
- DL-1B with lead-in: axitinib 3 mg oral BID followed by avelumab 10 mg/kg IV Q2W in combination with axitinib 3 mg oral BID, or

- DL1: avelumab 10 mg/kg IV Q2W in combination with axitinib 5 mg oral BID, or
- DL-1A: avelumab 5 mg/kg IV Q2W in combination with axitinib 5 mg oral BID, or
- DL-1B: avelumab 10 mg/kg IV Q2W in combination with axitinib 3 mg oral BID.

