**Start and end dates of study treatment:**

The date/time of first dose of study treatment is the earliest date/time of the first non-zero dose date/time for the study drugs in the combination.

The date/time of last dose of study treatment is the latest date/time of the last non-zero dose date/time for the study drugs in the combination.

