## **3.5. Safety Endpoints**

### **3.5.1. Adverse events**

#### **Treatment-Emergent Adverse Events**

Treatment-emergent adverse events (TEAEs) are those events with onset dates occurring during the on-treatment period for the first time, or if the worsening of an event is during the on-treatment period.

**On-treatment period** is defined as the time from the first dose of study treatment through minimum (30 days + last dose of study treatment, start day of new anti-cancer drug therapy – 1 day). The start day of new anti-cancer drug therapy after the first dose of study treatment is derived as outlined in Section 5.2.5.

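### For DL1 with lead-in, the SAP's overall safety summaries mix the axitinib-only week with the combination period, and no summary separates the lead-in as Protocol 9.6 says it will be

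*SAP*

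**What the plan says.** SAP 3.4.1 defines one treatment group as "DL1 with lead-in: axitinib 5 mg oral BID followed by avelumab 10 mg/kg IV Q2W in combination with axitinib 5 mg oral BID". The axitinib-only week is thus part of that group's study treatment. The same section dates the first dose of study treatment: it "is the earliest date/time of the first non-zero dose date/time for the study drugs in the combination".

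Three definitions rest on that date:
- The on-treatment period (SAP 5.2.7): "On-treatment period is defined as the time from the first dose of study treatment through minimum" of 30 days after the last dose and the day before new anti-cancer drug therapy.
- TEAEs (SAP 3.5.1), which "are those events with onset dates occurring during the on-treatment period for the first time", or which worsen in that period.
- Study day (SAP 5.2.4): "Start day of study treatment is the day of the first dose of study treatment".

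SAP 6 splits summaries into DL1, DL1 with lead-in, and both combined. Protocol 9.6 contains two separate commitments: "Safety data collected during the lead-in PK period will be reported separately", and then "All safety data collected through 90 days after the last administration of study drug will be listed".

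Two other SAP rules are relevant. Step 2 of Table 10 (Appendix 1) opens the irAE window at the first study drug administration, and SAP 3.4.1 lets study drug mean either agent. SAP 6.5.3.6 sets the Cycle 1 avelumab delay to the day of the first avelumab dose minus 1, without naming the day count.

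**The concern.** The overall safety profile of the combination is a secondary objective. Events, laboratory grades and ECG values that arise before a patient has received any avelumab are counted in tables that describe that combination. SAP 6.6 lists no AE, worst-grade laboratory or notable-ECG summary that is limited to the lead-in or excludes it. Protocol 9.6.2.1 also foresees AE summaries by cycle, which might have isolated the lead-in, but SAP 6.6.1.1 lists none. A reader of the lead-in or combined column could not tell from the summaries which findings belong to which period.

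Two lesser gaps come from the same lack of an avelumab anchor: an event before any avelumab is eligible as an irAE by onset, and the Cycle 1 delay can be read in two ways.

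**Working it through.** **Plan's own figure first.** SAP 6.5.3.6 gives a worked example of delay after Cycle 1. The formula is date difference minus 14. Avelumab on Day 1 and then on Day 16, 17 or 18 gives 15 − 14 = 1, 16 − 14 = 2 and 17 − 14 = 3 days. This reproduces the stated 1–3 days.

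**When the window opens.** The lead-in lasts 7 days (SAP 2.2), so its first day is study day 1 and Cycle 1 Day 1 is study day 8. The on-treatment period opens 7 days before any avelumab.

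**What the window takes in, per lead-in patient.**
- ECG (Protocol Schedule of Activities, ECG footnotes for the treatment and End of Treatment periods): Lead-in Day 7 pre-dose and 2 hours; Cycle 1 Day 1 before and after infusion; Cycle 4 Day 1 pre-dose and 2 hours; End of Treatment. That is 7 scheduled on-treatment time points. The first three precede avelumab: 3/7 = 43%.
- Laboratory: Cycle 1 Day 1 samples are scheduled before avelumab, which is given after that day's assessments (Protocol 5.3.3.1). That is one scheduled on-treatment draw before avelumab.
- AEs: any onset or worsening in the 7 days.

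**Share of the combined column, assuming 40 expansion patients.**
- 6 lead-in patients (the DLT-evaluable number that completes dose finding, SAP 5.1.2): 6/46 = 13%.
- 6 plus the optional 8 PK patients (SAP 5.1.1): 14/54 = 26%.
- 15, from the SAP total of about 55 less 40: 15/55 = 27%.

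The documents do not give the actual number.

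**Sensitivity of one table row.** If one patient's only event in a row began in the lead-in, the lead-in column moves by 1/15 = 6.7 to 1/6 = 16.7 points. The combined column moves by 1/55 = 1.8 to 1/46 = 2.2 points. These figures are simply 1/n. They do not say how many rows are affected.

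**irAE window.** Table 10 requires in turn a listed term, onset from the first study drug dose, treatment of the event, a qualifying concomitant medication, and an etiology or pathology check. No step asks whether avelumab had been given.

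**Cycle 1 delay for an on-schedule lead-in patient.**
- Study-day reading: 8 − 1 = 7, in the category of 7 or more days.
- Cycle-day reading: 1 − 1 = 0, no delay.
- Counted from planned Cycle 1 Day 1: 8 − 8 = 0. First avelumab on study day 9 or 11 gives 1 or 3 days.

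**The case against.** The strongest reply is that much separation already exists. The DL1 column contains no lead-in data and, with 40 expansion patients, holds 40/55 = 73% to 40/46 = 87% of patients. SAP 6.6.1.1 tabulates TEAEs related to avelumab and to axitinib separately. By-visit statistics keep the lead-in visits apart, and SAP 5.2.4 adds: "The study day will be displayed in all relevant data listings". Counting TEAEs from the first dose of either drug also fits the safety analysis set and the AE recording period in the protocol. Protocol 9.6 does not prescribe a particular table, the SAP may modify protocol plans (SAP 2), and its version history is redacted.

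Most of this stands, and it limits the point. It does not remove it. The DL1 with lead-in column separates a group of patients, whereas Protocol 9.6 separates a period of data. Listings answer a different sentence of Protocol 9.6. The per-drug tables sort events by attributed cause, not by when they began.

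Four stronger readings are tempting and are not supported:
- That starting the on-treatment period at the first axitinib dose is itself an error. It is a sound whole-period definition; the gap is the missing split.
- That the SAP made an undeclared change. The visible text declares none, but the redaction prevents a judgement.
- That irAE counts will be materially inflated. An event would have to begin within about 7 days and pass every step of Table 10 and the medical review that follows it.
- That every lead-in patient will be reported as delayed by 7 or more days. The example in SAP 6.5.3.6 calls an avelumab dosing day Day 1, which favours the cycle-day reading. The example could describe a patient without a lead-in, so it does not settle the matter.

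**Conclusion.** The point holds for the TEAE, worst-grade laboratory and notable-ECG summaries in the DL1 with lead-in and combined columns. Followed as written, the SAP mixes the two periods there and provides no summary that answers Protocol 9.6. It should be corrected, but its reach is limited. The primary DLT analysis starts at the first avelumab dose and infusion-related reactions are tied to the avelumab infusion, so neither is affected.

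The size is known only in outline: 3 of 7 scheduled ECG time points and one laboratory draw per lead-in patient, and roughly 13% to 27% of the combined column. These rest on a 7-day lead-in, 40 expansion patients and, for ECGs, follow-up to End of Treatment. They count time points and patients, not abnormal findings.

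The irAE gap is real in the text, with few cases expected to change. The delay point is an ambiguity of wording and nothing more.

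**What to change.** For DL1 with lead-in:

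1. Keep the whole-period tables. Add a lead-in AE summary, from the first axitinib dose to before the first avelumab dose. Add a combination-period AE summary, with onset or worsening on or after the first avelumab dose, among patients who received avelumab.
2. Apply the same split to the worst-grade laboratory and notable-ECG tables, assigning values taken before the first infusion to the lead-in. The split alone leaves baseline before axitinib (SAP 3.4.1), so changes in the combination period would still include the axitinib effect. State that this baseline is used, or add the last pre-avelumab value as a second reference.
3. If the departure from Protocol 9.6 is intended, declare it in the SAP.
4. In Step 2 of Table 10, require onset on or after the first avelumab dose.
5. As a clarification, state in SAP 6.5.3.6 that the Cycle 1 avelumab delay is counted from planned Cycle 1 Day 1, and whether a Cycle 1 Day 1 visit postponed under Protocol 7.2.1 counts as delay.

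The cost is SAP wording and a few extra tables for about 6 to 15 patients. No new data are needed.

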3.4. Recommended Phase 2 Dose Definition

The RP2D is the dose of avelumab and axitinib in combination chosen for further studies based on Phase 1 study results. If the MTD proves to be clinically feasible for long-term administration in a reasonable number of patients, then this dose usually becomes the RP2D. Further experience with the MTD may result in a RP2D dose lower than the MTD. Attention will be given to the percentage of patients that discontinue treatment due to treatment-related AEs, especially (both early and late occurring) immune-related (dose-limiting) toxicities.

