8.2. Reporting Period

For SAEs, the active reporting period to Pfizer or its designated representative begins from the time that the patient provides informed consent, which is obtained prior to the patient's participation in the study, ie, prior to undergoing any study-related procedure and/or receiving investigational product, through and including 90 calendar days after the last administration of the study treatment.

SAEs occurring to a patient after the active reporting period has ended should be reported to the sponsor if the investigator becomes aware of them; at a minimum, all SAEs that the investigator believes have at least a reasonable possibility of being related to investigational product are to be reported to the sponsor.

AEs (serious and non-serious) should be recorded on the CRF from the time the patient has taken at least one dose of study treatment through and including 90 calendar days after the last administration of study treatment. If a patient begins a new anticancer therapy, the AE reporting period for nonserious AEs ends at the time the new treatment is started. Death must be reported if it occurs during the SAE reporting period after the last dose of study treatment, irrespective of any intervening treatment.

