### 6.6.1. Adverse events

Treatment-emergent adverse events (TEAEs) are those events with onset dates occurring during the on-treatment period for the first time, or if the worsening of an event is during the on-treatment period as defined in Section 3.5.1.

All analyses described below will be based on TEAEs (started during the on-treatment period) if not otherwise specified. The AE listings will include all AEs (whether treatment-emergent or not). AEs outside the on-treatment period will be flagged in the listings.

- **Related Adverse Events:** adverse events with relationship to study treatment (as recorded on the AE eCRF page, Relationship with study treatment = Related) reported by the investigator and those of unknown relationship (ie, no answer to the question ‘Relationship with study treatment’). Related AEs are those related to any study drug (ie, at least one of the study drugs).
- **Serious Adverse Events (SAE):** serious adverse events (as recorded on the AE eCRF page, Serious Adverse Event = Yes).
- **Adverse Events Leading to Dose Reduction:** adverse events leading to dose reduction of study treatment (as recorded on the AE eCRF page, Action taken with study treatment = Dose reduced).
- **Adverse Events Leading to Interruption of Study Treatment:** adverse events leading to interruption of study treatment (as recorded on the AE eCRF page, Action taken with study treatment = Drug interrupted). The eCRF does not allow for a clear separation between interruption of an infusion and delays of administration for a parenteral drug as both are recorded using the same term on the eCRF (“Drug interrupted”). IRRs will be excluded in the analysis of AEs leading to Drug Interruption in case they only led to an interruption of the infusion.

- **Adverse Events Leading to Permanent Treatment Discontinuation:** adverse events leading to permanent discontinuation of study treatment (as recorded on the AE eCRF page, Action taken with study treatment = Drug withdrawn).
- **Adverse Events Leading to Death:** adverse event leading to death (as recorded on the AE eCRF page, Outcome = Fatal, as well as AEs of Grade 5).
- **Immune-related Adverse Events (irAE):** irAEs (as identified according to the methodology outlined in Appendix 1 for a pre-specified search list of MedDRA PTs, documented in the Safety Review Plan and finalized for analysis of the current studies data prior to DB lock)

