**Table 10. Case Definition for irAEs**

Step	Selection Criteria	Additional Notes
1	Event selected based on a list of pre-specified MedDRA PTs within clusters. These are included in the SRP as Tier1 events (Immune-mediated xxxx). If AE matches the list then it is in for the next step	
2	AE onset during 1 st study drug administration or anytime thereafter through 90 days after last dose of study treatment.	This is regardless of start of new anti-cancer drug therapy and regardless of TEAE classifications
3	Answer in the AE eCRF page to ‘Was another treatment given because of the occurrence of the event’ is ‘YES’	
4	AE treated with corticosteroids or other immunosuppressant therapy. For endocrinopathies only: AE required hormone replacement	Look in the conmed pages for AE identifiers that match the AEs from Step 3. For each of such AEs if A) OR B) below are met then the AE is in for the next step A) conmed ATC code is in (H02A, H02B, H02C, D07, A01AC, S01BA, S01BB, L04AA, L04AB, L04AC, L04AD, L04AX) and AE PT is in any of the irAE clusters. B) conmed ATC code is in (H03A, H03B) and AE PT is in one of the irAE clusters associated with “Immune-mediated endocrinopathies”

5
	
A) No clear etiology (other than immune mediated etiology)
 
B) Histopathology / biopsy consistent with immune-mediated event
 
Event is in if          [Answer to 5B1 and 5B2 is YES (regardless of answer to 5A)]          OR          [Answer to 5B1 is YES AND answer to 5B2 is NO AND answer to 5A is NO]          OR          [Answer to 5B1 is NO AND answer to 5A is NO]
	
A) From the AE eCRF page          Is the AE clearly related to an etiology other than immune-mediated etiology? Yes / No          If answer is Yes, check all that apply:
 
 
• Underlying malignancy / progressive disease.
 
• Other medical conditions.
 
• Prior or concomitant medications / procedures.
 
• Other. Specify.
 
 
B) From the AE eCRF page          B1) Was there a pathology /histology evaluation performed to investigate the AE? Y/N          B2) If answer to the above is Yes, does the pathology/histology evaluation confirms an immune mediated mechanism for the AE? Y/N          B3) If pathology / histology evaluation performed to investigate the AE, provide summary of relevant findings of the pathology /histology report. (Free Text)

----------	---	--

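### SAEs and Grade 3 or higher AEs with onset after the 30-day window appear only in listings, and the SAP does not settle whether the irAE tables stop at 30 days or run to 90

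*SAP*

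**What the plan says.** **Collection.** Protocol 8.2 records serious and non-serious AEs "through and including 90 calendar days after the last administration of study treatment". Non-serious reporting ends earlier if a new anticancer therapy begins. Protocol 9.6 then states: "All safety data collected through 90 days after the last administration of study drug will be listed".

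**Summary window.** SAP 5.2.7 (and 3.5.1) ends the on-treatment period at the "minimum (30 days + last dose of study treatment, start day of new anti-cancer drug therapy – 1 day"). The section opens with a default that allows exceptions, "Safety endpoints will be summarized based on the on-treatment period unless otherwise specified", and closes with a flat one: "Safety data collected outside the on-treatment period as described above will be listed and flagged in listings but not summarized".

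**AE and SAE tables.** SAP 6.6.1 sets the same default: "All analyses described below will be based on TEAEs (started during the on-treatment period) if not otherwise specified". The Grade 3 or higher rows in 6.6.1.1 are TEAE rows. Section 6.6.3 gives frequencies for treatment-emergent SAEs only, and flags later ones in the listing. Section 6.6.2 tabulates all deaths, with deaths within 30 days of the last dose as a separate row.

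**irAEs.** Step 2 of Table 10 in SAP Appendix 1 accepts onset through 90 days after the last dose and comments: "This is regardless of start of new anti-cancer drug therapy and regardless of TEAE classifications". The closing paragraph of Appendix 1 says that the data set produced this way, after medical review, is what the irAE analyses rest on. Section 6.6.4 describes the irAE tables without a treatment-emergent qualifier and without a time window. It mentions late onset only as a listing flag.

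**The concern.** Safety is the primary objective of this study, and an immune checkpoint antibody can cause toxicity after dosing stops; Protocol 5.3.5.4 itself warns that irAEs may appear at any time after the first avelumab dose. The trial collects 90 days of post-treatment safety data, but its AE and SAE frequency tables use at most the first 30. A reader who takes event rates from the tables would miss serious and severe events that the trial recorded.

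The irAE tables raise a different problem. The case definition reaches 90 days and overrides TEAE status, while the general rules point to 30 days and name no exception. Two programmers could each follow the SAP and report different irAE counts.

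**Working it through.** The plan gives no figure to reproduce, so this is a comparison of windows.

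**1. The windows.** Let L be the last dose of study treatment. SAP 3.4.1 makes this the later of the two drugs' last non-zero doses. Let N be the start of a new anti-cancer drug. All days are counted from L.

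- SAE collection: day 90 (Protocol 8.2).
- Non-serious AE collection: day 90 or N, whichever is earlier (Protocol 8.2).
- AE and SAE tables: min(30, N − 1) (SAP 5.2.7).
- irAE case definition: day 90, whatever N is (Table 10, Step 2).

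If no new drug starts before day 31, the tables stop at day 30. That leaves 90 − 30 = 60 days outside them, and 60/90 = 67% of the calendar window.

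If a new drug starts on day 10 (an assumed value, for illustration), the tables stop at day 9. For SAEs, 90 − 9 = 81 days are then outside. Required non-serious AE collection has also ended. Because Protocol 8.3.1 puts AEs of special interest under the same reporting rules, only serious irAEs are sure to be recorded after that point.

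If avelumab has stopped but axitinib continues, L has not been reached. The patient is still on treatment, and the event is tabulated under any reading unless a new anti-cancer drug has started.

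**2. An event with onset on day 45, no new therapy.**

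| Event | Collected | Listing | Frequency table |
|---|---|---|---|
| SAE, not an irAE | yes | yes, flagged (6.6.3) | none (6.6.3 covers treatment-emergent SAEs) |
| Non-serious Grade 3 or higher AE, not an irAE | yes | yes, flagged (6.6.1) | none (6.6.1.1 rows are TEAEs) |
| Fatal AE, not an irAE | yes | yes | all deaths (6.6.2), but not TEAEs leading to death (6.6.1.1) |
| AE meeting Table 10 | yes | yes, flagged (6.6.4) | depends on the reading |

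**3. The two irAE readings.**

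- *Tabulate to day 90.* Appendix 1 sets TEAE status aside and supplies the data set for the irAE analyses. Section 6.6.3 restricts SAEs to treatment-emergent events and 6.6.4 does not do this for irAEs. The overview table in 6.6.1.1 likewise has a row for serious TEAEs but a plain irAE row.
- *Tabulate to day 30.* The 6.6.1 default covers the analyses below it, and irAEs are one of the categories listed there. The last sentence of 5.2.7 makes no exception. The late-onset flag in 6.6.4 is the same device that 6.6.3 uses for SAEs, whose tables are limited to the on-treatment period.

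The first reading is the better one, but neither 5.2.7 nor 6.6.4 says so.

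**4. Weight of one patient.** SAP 5.1.1 expects at most about 55 patients, up to about 40 of them in expansion. Moving one patient in or out of a row changes a rate by 1/55 = 1.8 percentage points overall, or 1/40 = 2.5 points in expansion.

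**The case against.** The strongest reply is that the SAP does what the protocol promised. Protocol 9.6 commits only to listing the 90-day data, and 9.6.2.1 places the emphasis on treatment-emergent events. In a descriptive study of about 55 patients with no hypothesis test, flagged patient-level listings lose no information, and events after day 30 may reflect later therapy. All of this stands: there is no breach of the protocol, and the treatment of late SAEs is an analysis choice. It does not supply a rate for late serious events, and it does not settle the irAE window.

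Three stronger readings are tempting, and the documents do not support them.

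- A reader might infer from the last sentence of 5.2.7 that nothing outside 30 days is ever summarized. The same section opens with an exception clause, 6.6.1 repeats one, and 6.6.2 tabulates all deaths.
- A reader might infer that late irAEs are lost from the tables. Appendix 1 makes their inclusion the more natural reading; the defect is that the SAP leaves it to inference.
- A reader might infer that the choice of RP2D rests on these tables and so misses late toxicity. Protocol 3.4 does draw attention to toxicities, "especially (both early and late occurring) immune-related (dose-limiting) toxicities", but the measure in that sentence is the percentage of patients who discontinue because of treatment-related AEs. An event that begins more than 30 days after both drugs have stopped can rarely cause a discontinuation. Protocol 3.1.1.2 bases the RP2D on all available data, and 9.7 provides for continuing safety review.

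**Conclusion.** The point holds in two parts.

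- **Late SAEs and Grade 3 or higher AEs.** Those with onset after the on-treatment period enter no AE or SAE frequency table, unless they are also tabulated as irAEs. Fatal outcomes still count among all deaths. This is permitted by the protocol but leaves delayed toxicity out of the reported rates.
- **irAEs.** The general rules and Appendix 1 are not reconciled, so irAE counts could differ by reading.

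The window at issue is 60 of 90 days when no new anti-cancer drug starts before day 31, and longer for SAEs when one does. The 67% is a share of calendar days, not of events. The documents give no late-event rates, so the number of patients affected cannot be derived. This is a cheap improvement in reporting and clarity, not an error that invalidates the plan.

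**What to change.** 1. In SAP 5.2.7 and 6.6.4, name irAEs as an exception to the on-treatment rule, and state that the irAE tables include every event meeting Table 10 with onset through 90 days after the last dose.
2. Add one supplementary frequency table of SAEs and Grade 3 or higher AEs with onset through 90 days after the last dose. Flag events that begin after new anti-cancer therapy, and footnote that non-serious AE collection stops when that therapy starts.
3. Keep the 30-day TEAE tables as primary.

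The cost is a short clarification in two sections and one extra table, with no new data collection. The downside is that days 31 to 90 may include effects of later therapy. The flag makes those events visible, and the footnote warns that the non-serious counts are incomplete after a switch.
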